### 3. Organ function and laboratory results

Patients must have the following laboratory values (obtained within 14 days of enrolment):

- a. Total serum bilirubin  $\leq 1.5 \times$  upper limit of normal (ULN)
- b. Alkaline phosphatase (ALP)  $\leq 2.5 \times$  ULN; if liver function abnormalities are due to the underlying malignancy and known bone metastases, then ALP must be  $\leq 5 \times$  ULN
- c. Serum aspartate aminotransferase (AST/SGOT) and alanine aminotransferase (ALT/SGPT)  $\leq 2.5 \times$  ULN; if liver function abnormalities are due to the underlying malignancy and known hepatic metastases, then AST and ALT must be  $\leq 5 \times$  ULN
- d. Serum creatinine  $\leq 1.5 \times$  ULN; or if serum creatinine  $> 1.5 \times$  ULN, then serum creatinine clearance (CrCl)  $\geq 50$  mL/min (estimated by Cockcroft-Gault formula)
- e. Potassium levels within normal limits or correctable with supplements
- f. Total calcium levels (corrected for serum albumin) within normal limits or correctable with supplements
- g. Magnesium levels within normal limits or correctable with supplements
- h. Phosphorus levels within normal limits or correctable with supplements
- i. Serum albumin concentration  $\geq 30$  g/L
- j. Patients with solid tumours must have:
  - Absolute neutrophil count (ANC)  $\geq 1.5 \times 10^9/L$
  - Haemoglobin (Hgb)  $\geq 10$  g/dL ( $\geq 100$  g/L)
  - Platelet count  $\geq 75 \times 10^9/L$  (without platelet transfusion or growth factor support in the preceding 7 days)
  - Partial thromboplastin time (PTT)  $\leq 1.5 \times$  ULN and international normalised ratio (INR)  $\leq 1.3$  (unless the patient is receiving therapeutic anticoagulants)

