Grade 3 or QTcF $\geq$ 500 ms as identified by the Investigator on the ECG.	
Omit dose administration. Monitor patient with frequent ECGs as indicated (e.g. hourly) until the QTcF has returned to <math>\leq</math> 480 ms. Further monitoring as clinically indicated. Exclude other causes of QTc prolongation such as hypokalaemia, hypo-magnesaemia and blood oxygenation status. Once QTcF prolongation has resolved, and if the QTcF prolongation was confirmed by central reading, patients may be re-treated at one lower dose level at the Investigator's discretion.
 
ECG monitoring must continue throughout the treatment period as follows:
 
 
• ECG monitoring assessments should be performed for 2 additional cycles at higher frequency as clinically indicated
 
• If the ECGs obtained in the first additional cycle after dose reduction are without any QTcF prolongation, then ECG monitoring in subsequent cycles will be continued as per the visit schedule.
 
• If the patient had an absolute QTcF <math>\geq</math> 480 ms and <math><</math> 500 ms, then ECG monitoring at a higher frequency will be continued for all subsequent cycles.
 
• Patients who experience absolute QTcF <math>\geq</math> 500 ms after one dose reduction will be discontinued from study.
 
 
Note:
 
 
• If QTcF <math>\geq</math> 500 ms result is observed in a patient during the study treatment, this event will be considered as a DLT. If Torsades de Pointes are observed in a patient, the patient will be discontinued from the study.
 
• Whenever QTcF <math>\geq</math> 500 ms result is observed, a plasma sample for determination of CB-103 concentration should be obtained and the time of sample collection noted.
 

 Common Terminology Criteria for Adverse Events (CTCAE Version 4.03)

 Exclude other causes of QTcF prolongation such as hypokalaemia, hypomagnesaemia and blood oxygenation status. Patients who develop hypokalaemia or hypomagnesaemia during the study should receive electrolyte replacement as soon as possible and should not receive further CB-103 dosing until the respective electrolytes are documented to be within normal limits.

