## 8.2.4 Laboratory Safety Assessments

Laboratory safety tests shall be performed at time-points specified in the Schedule of Assessments ([Appendix 1](#) and [Appendix 2](#)).

Additional blood or urine samples may be taken at the discretion of the Investigator if the results of any test fall outside the reference ranges, or clinical symptoms necessitate additional testing to monitor patient's safety. Where the clinical significance of abnormal

lab results is considered uncertain, screening lab tests may be repeated before enrolment to confirm eligibility.

In the event of unexplained abnormal clinically significant laboratory test values, the tests should be repeated immediately and followed up until they have returned to the normal range and/or an adequate explanation of the abnormality is found. Results of clinical laboratory testing will be recorded on the eCRF.

Samples for the following blood and urine laboratory tests will be collected as specified in the Schedule of Assessments ([Appendix 1](#) and [Appendix 2](#)) and sent to the local laboratory for analysis.

- **Haematology:** Haemoglobin, haematocrit, erythrocytes (RBC), reticulocyte count, platelets, leukocytes (WBC), differentials (counts): neutrophils, eosinophils, lymphocytes, monocytes, basophils.
- **Coagulation:** prothrombin time (expressed as INR) and activated partial thromboplastin time (aPTT).
- **Blood chemistry:** AST, ALT, total and conjugated bilirubin, ALP, gamma-glutamyl-transferase ( $\gamma$ -GT), creatine phosphokinase (CPK), albumin, creatinine, urea nitrogen, total protein, sodium, chloride, calcium, bicarbonate, phosphate, potassium, triglycerides, total cholesterol, glucose, C-reactive protein (CRP), lipase, urate and lactate dehydrogenase.
- **Serology:** human immunodeficiency virus (HIV), hepatitis B (HBV) or C (HCV).
- **Pregnancy test:** All women of childbearing potential (including those who have had a tubal ligation) will have serum or urine pregnancy tests at the time-points specified in the Schedule of Assessments ([Appendix 1](#) and [Appendix 2](#)). Pregnancy tests will also be done whenever one menstrual cycle is missed during the active treatment period (or when potential pregnancy is otherwise suspected) to confirm the patient has not become pregnant during the study.

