-  Ophthalmological exams: they will be performed by an ophthalmologist/eye doctor at screening, End of Treatment and when clinically indicated. Refer to [Section 8.2.2.2](#)
-  Ophthalmological exams: will be done at the safety follow-up if the patient had ocular symptoms during the treatment phase
-  Clinical chemistry/Haematology/coagulation will be performed locally; at screening (within 14 days of C1D1), and at the indicated visits. Refer to [Section 8.2.4](#) of the protocol for the testing required. May be performed within a window of  $\pm 24$  hours during the DLT period and throughout all treatment cycles.
-  PK time sampling: blood sampling will be collected as per the schedule and time window indicated in [Section 8.4](#) of the protocol. Changes to the PK sampling scheme may be required based on emerging data. In case of twice daily intake of CB-103 the sampling schedule is slightly adjusted for cycle 1 (refer to [Section 8.4.1](#))
-  Stool specimen collection: only one sample is to be possibly collected during cycle 2 and 3.
-  Chest X-ray: a baseline chest x-ray should be performed and be repeated if clinically indicated. If a chest CT is performed at baseline to assess tumour lesions, then a chest X-ray may not be required.
-  Survival follow-up: it is planned for one year, every three months, after the End-of-Study visit or after the last treatment cycle (if outside of the 6 cycles period).
-  Between the signature of the ICF and the initiation of CB-103, only the SAEs caused by study-related procedures will be reported; any other AEs will be only recorded on the Medical History in the eCRF. After initiation of CB-103, all AEs/SAEs will be reported until four weeks after the last dose of CB-103.
-  Archival tumour biopsy tissue (Solid Tumour): for the patients enrolled in Part A (dose-escalation) it should be not older than 6 months prior to screening and if not available a pre-dose fresh tumour biopsy must be taken. If the lesion is not accessible for a fresh tumour biopsy, a liquid biopsy may be used after confirmation with the Sponsor.

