-  Ophthalmological exams: they will be performed by an ophthalmologist/eye doctor at screening, End of Treatment and when clinically indicated. Refer to [Section 8.2.2.2](#).
-  Ophthalmological exams: will be done at the safety follow-up if the patient had ocular symptoms during the treatment phase.
-  Clinical chemistry/Haematology/coagulation: will be performed locally; at the screening (within 14 days of C1D1), and at the indicated visits. Refer to [Section 8.2.4](#) of the protocol for the testing required. May be performed within a window of  $\pm 24$  hours throughout all treatment cycles.
-  PK time sampling: blood sampling will be collected as per the schedule and time window indicated in [Section 8.4](#) of the protocol. Changes to the PK sampling scheme may be required based on emerging data. In case of twice daily intake of CB-103 the sampling schedule is slightly adjusted for cycle 1 (refer to [Section 8.4.1](#)).
-  Chest X-ray: a baseline chest x-ray should be performed and be repeated if clinically indicated. If a chest CT is performed at baseline to assess tumour lesions, then a chest X-ray may not be required.
-  Survival follow-up: it is planned for one year, every three months, after the End-of-Study visit or after the last treatment cycle (if outside of the 12 cycles period), then every 6 months for the second year.
-  Between the signature of the ICF and the initiation of CB-103, only the SAEs caused by study-related procedures will be reported; any other AEs will be recorded on the Medical History in the eCRF. After initiation of CB-103, all AEs/SAEs will be reported until 4 weeks after the last dose of CB-103.
-  Fresh tumour biopsy (Solid Tumour): to be collected pre-dose during the screening/BL period, then on-treatment at C2D15  $\pm 3$  days and at disease progression or when clinically indicated. The pre-dose fresh biopsy is not required if obtained during the pre-screening. If the lesion is not accessible for a fresh tumour biopsy, a liquid biopsy may be used after confirmation with the Sponsor.

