## 1. Source Documents

The SAP is based on the following documentation and is for the Part A of the study.

Document	Date	Version
Protocol	03 August 2020	4.1
eCRF	17 May 2021	4.0-4.2

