### 5.7.2 Laboratory Evaluations

Laboratory values will be graded by NCI CTCAE version 4.03 (or higher), if no grading exists values will be classified into low/normal/high based on laboratory normal ranges. Each parameter will be presented by descriptive statistics at each visit including change from baseline (screening). Shift tables for CTCAE grades and normal ranges will be presented.

All values should be reported in SI units (if applicable), results reported in non-SI unit should be converted to SI unit. Missing values will be excluded.

Only patients with non-missing change from baseline data at the visit will be included in the post-baseline summary statistics at the visit. Baseline is defined as the last measurement prior to dosing.

Results from the following laboratory parameters will be summarized by cohort and time point:

**Haematology:** Haemoglobin, haematocrit, erythrocytes (RBC), reticulocyte count, platelets, leukocytes (WBC), differentials (counts): neutrophils, eosinophils, lymphocytes, monocytes, basophils.

**Coagulation:** Prothrombin time expressed as International normalized ratio (INR), activated partial thromboplastin time (aPTT).

**Biochemistry:** Total protein, albumin, alkaline phosphatase, total bilirubin, calcium, cholesterol, chloride, creatine kinase, aspartate aminotransferase (AST), alanine aminotransferase (ALT), lactate dehydrogenase, C-reactive protein (CRP), lipase, pancreatic amylase, glucose, inorganic phosphorus, magnesium, potassium, sodium, triglycerides, urea/blood urea nitrogen, uric acid, creatinine (creatinine clearance estimated according to the Cockcroft-Gault formula).

Aspartate aminotransferase (AST), alanine aminotransferase (ALT), total and conjugated bilirubin, albumin, alkaline phosphatase (ALP), gamma-glutamyl-transferase (GGT), amylase, bicarbonate, calcium, chloride, total cholesterol, creatine phosphokinase (CPK), C-reactive protein (CRP), creatinine, blood urea nitrogen (BUN), glucose, phosphate, lactate dehydrogenase (LDH), lipase, magnesium, potassium, total protein, sodium, triglycerides, urate.

**Urine from dipstick:** Protein, glucose, ketones, red (RBC) and white blood cells (WBC), pH, specific gravity.

**Detailed Urinalysis** (if clinically significant positive results from the dipstick): bacteria, casts (RBC, haemoglobin, hyaline, WBC), RBC, WBC, mucus, oxalates, epithelial cells, renal and squamous epithelial cells, uric acid crystals, unspecified crystals, urate, yeast.

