**Cardiac markers:** Serum troponin, N-terminal pro-peptide BNP

Laboratory parameters other than cardiac markers are assessed at following time points:

- At screening
- During Cycle 1 on Day 1, Day 3 (only Part A), Day 8, Day 15 and Day 22
- During other Cycles on Day 1 and Day 15
- At EOT visit

Cardiac serum markers are to be collected:

- At baseline
- During Cycle 1: on Day 22
- During other Cycles on Day 1 and Day 15
- At EOT visit

Absolute values and changes values from baseline for haematology, biochemistry and coagulation assessments will be summarized (cf. notes in section 4.1).

Shift tables for Out of Normal Range Results for haematology, biochemistry and coagulation assessments will be summarized.

Shift tables for CTCAE grades for haematology, biochemistry and coagulation assessments will be summarized.

Local dipstick urinalysis ( ) as well as results will be summarized according to being normal or abnormal.

All laboratory results will be listed.

A separate listing for abnormal lab values (Grade 3 and higher, and low/high values) will be presented.

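### The protocol's blood chemistry list (8.2.4) omits magnesium, so the dosing hold for hypomagnesaemia has no scheduled on-treatment test behind it

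*Protocol*

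**What the plan says.** **Entry.** Criterion 3g, in the synopsis and in Protocol 6.1.1, asks for "Magnesium levels within normal limits or correctable with supplements", with laboratory values obtained within 14 days of enrolment.

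**On treatment.** Table 8 in Protocol 7.4.6.1.5 covers QTcF prolongation. Its footnote 2 names hypokalaemia and hypomagnesaemia among the other causes to exclude. It then says that patients who develop either during the study "should not receive further CB-103 dosing until the respective electrolytes are documented to be within normal limits".

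**Which tests are run, and when.** Appendix 1 footnote 13 (Part A) and Appendix 2 footnote 12 (Part B) place chemistry at screening and the marked visits, in the Part B wording "at the screening (within 14 days of C1D1), and at the indicated visits". Both refer to Protocol 8.2.4 for the content of the panel. The middle of that list reads "total protein, sodium, chloride, calcium, bicarbonate, phosphate, potassium, triglycerides, total cholesterol, glucose". Magnesium is not there, nor in any other panel of 8.2.4.

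**Analysis.** SAP 5.7.2 names magnesium in both of its biochemistry lists, the first of which contains "inorganic phosphorus, magnesium, potassium, sodium, triglycerides", for summary by cohort and time point. On scope, SAP section 1 states: "The SAP is based on the following documentation and is for the Part A of the study". It gives protocol version 4.1 as its source. The protocol under review is version 4.3.

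**The concern.** The protocol makes a low magnesium a reason to stop dosing, but the panel it prescribes would not routinely find one. Footnote 2 treats potassium and magnesium alike, yet only potassium is on the list.

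The rule has a purpose. Protocol 2.5.2.1 reports QTc prolongation in dogs at the higher doses and gives hERG inhibition as the most likely mechanism. Protocol 2.5.6 reports treatment-related nausea in 24% and diarrhoea in 20% of the first 41 patients. The management plan in 7.4.7 answers these with metoclopramide and loperamide, warns of Torsades de Pointes under certain conditions, and asks for electrolytes to be followed and corrected. A site that follows 8.2.4 to the letter would do this without a routine magnesium value.

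There is also a smaller reporting consequence. If magnesium is collected only when someone chooses to order it, the by-visit magnesium summaries planned in the SAP would describe a selected set of patients.

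**Working it through.** No figure in the plan needs reproducing. The check compares lists and counts scheduled draws.

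**1. Count the 8.2.4 blood chemistry list.** AST, ALT, total bilirubin, conjugated bilirubin, ALP, gamma-GT, CPK, albumin, creatinine, urea nitrogen, total protein, sodium, chloride, calcium, bicarbonate, phosphate, potassium, triglycerides, total cholesterol, glucose, CRP, lipase, urate, LDH. That is 24 analytes, without magnesium.

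**2. Compare with the chemistry entry criteria 3a to 3i.** These need 10 analytes: bilirubin, ALP, AST, ALT, creatinine, potassium, calcium, magnesium, phosphorus and albumin. Nine are in 8.2.4 (phosphorus as phosphate). Magnesium is the only one missing.

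| Electrolyte | Entry criterion | Named in Table 8 footnote 2 | In 8.2.4 list |
|---|---|---|---|
| Potassium | 3e | yes | yes |
| Calcium | 3f | no | yes |
| Magnesium | 3g | yes | **no** |
| Phosphorus | 3h | no | yes |

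**3. Compare with the SAP.** The second biochemistry list in SAP 5.7.2 has 26 analytes. It equals the 24 of 8.2.4 plus magnesium and amylase, and nothing in 8.2.4 is absent from it.

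**4. Count the scheduled on-treatment chemistry draws.**
- Part A (Appendix 1): Cycle 1 Days 1, 3, 8, 15 and 22 give 5. Cycles 2 to 6, Days 1 and 15, give 5 × 2 = 10. Total 5 + 10 = 15.
- Part B (Appendix 2): Cycle 1 Days 1, 8, 15 and 22 give 4. Cycles 2 to 6 give 5 × 2 = 10. Subtotal through Cycle 6: 14. Protocol 8.1 moves visits to every 4 weeks after Cycle 6, so Cycles 7 to 12 add 6. Total 14 + 6 = 20.
- If the Cycles 3 to 12 columns of Appendix 2 were read literally, with two draws per cycle, the Part B total would be 4 + 11 × 2 = 26. The choice of reading does not affect the finding.

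**5. Result.** The protocol lists magnesium at 0 of 15 Part A draws and 0 of 20 Part B draws.

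**6. What remains to trigger the hold.** Three routes are left: the work-up at QTcF ≥ 500 ms in Table 8; electrolyte follow-up when metoclopramide or loperamide is used (7.4.7); and additional samples at the investigator's discretion (8.2.4), after an out-of-range result or symptoms. Each starts from an event or a judgement, not from the calendar.

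**The case against.** **Screening is covered.** A reader might infer that patients enter with magnesium unchecked. The documents do not support this. Criterion 3g cannot be met without a value, and Protocol 8.10.1 requires every eligibility criterion to be confirmed. This objection stands, and it confines the gap to the treatment period.

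**The hold may be narrower than it looks.** Footnote 2 is attached to the QTcF-prolongation heading. If it applied only after prolongation, the test would be prompted by the event, because the row for QTcF ≥ 500 ms already tells sites to exclude hypomagnesaemia. That reading is possible. However, the sentence on withholding speaks of patients who develop the abnormality during the study and sets no QTcF condition. Potassium, governed by the same sentence, is tested routinely.

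**The SAP does not schedule blood draws.** SAP 5.7.2 says "Laboratory parameters other than cardiac markers are assessed at following time points" and gives days that match the Part A chemistry draws. A reader might infer that magnesium is therefore sampled at all 15. The SAP plans summaries, and its time-point lists are not a faithful copy of the protocol: it puts the Cycle 1 cardiac markers on Day 22, whereas Appendix 1 shows Day 15. It also cites an older protocol version. It does postdate version 4.3 (29 April 2022 against 28 May 2021) and declares no change to the planned analysis. Its lists are supporting evidence of an oversight in 8.2.4 and no more.

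**Other safeguards exist.** There are QTcF entry limits, restrictions on QT-prolonging drugs and central alerts at QTcF ≥ 500 ms. No QTc prolongation was reported in the 41 patients treated by 20 August 2020. These lower the urgency. They do not supply the magnesium value the hold needs.

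**Conclusion.** The inconsistency is real and rests on the protocol alone. Section 8.2.4, cited by both schedules, leaves out an analyte that criterion 3g requires at entry and that Table 8 footnote 2 makes a condition of further dosing. The gap is the absence of any scheduled on-treatment magnesium: 0 of 15 draws in Part A through Cycle 6 and 0 of 20 in Part B through Cycle 12. It is preventive in nature and should be fixed at the next amendment.

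This assumes that 8.2.4 is the operative list, as the schedules indicate, and that the second sentence of footnote 2 applies generally.

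A reader might go further in two ways that the documents do not support:
- **That sites do not measure magnesium on treatment.** The eCRF is not available, and its appearance in both SAP lists may mean that it is collected in Part A. For Part B the protocol schedules none, and the available SAP does not extend that far. Protocol section 10 foresees SAPs for each part, so the lack of a Part B SAP here proves nothing.
- **That patients have been harmed or are at a quantifiable risk.** The documents give no frequency of low magnesium, so no number of patients can be attached.

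Whether an abnormal but correctable value at entry should be normal before the first dose, and when Part B ECGs are taken relative to dosing, are separate design choices. This finding does not bear on them.

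**What to change.** Add magnesium to the blood chemistry list in Protocol 8.2.4. Because both schedules refer to that list, the one edit places magnesium at screening and at every scheduled chemistry draw in Parts A and B. It also brings 8.2.4 into line with criterion 3g, Table 8 footnote 2 and SAP 5.7.2. No change to the eligibility criteria is needed.

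The cost is one extra analyte on samples already drawn and sent to the local laboratory, with no new visit or sample, written into the next amendment. Routine testing may reveal low values that would otherwise go unnoticed, each of which would trigger the existing hold, so some additional dose interruptions are possible. If the eCRF already has a magnesium field, the amendment only corrects the protocol text. If not, the field must be added.

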### 4. Contraceptive measures

- a. Women of childbearing potential (WOCBP, for definition see Section 6.2) must have a serum pregnancy test performed within a maximum of 7 days before start of study treatment, and a negative result must be documented before start of study treatment.
- b. Women of childbearing potential and men must agree to use at least two highly effective forms of contraception (i.e., two of the following – oral contraception, injectable contraceptives, mechanical contraception including a condom for the partner, or an intrauterine coil) and must continue using them throughout the entire clinical trial period and for 90 days post-treatment completion (duration of

3 ovulatory cycles). Contraception must start from the day of 1st administration of CB-103.

- c. Men whose partners could be of childbearing potential must routinely use a condom throughout the entire clinical trial period and for 90 days post-treatment completion (duration of sperm turnover). The partner should also use a reliable form of contraception such as the oral contraceptive pill or an intrauterine device.
- d. Azoospermic males and females with sterilisation (e.g. tubal ligation) are exempt from contraceptive requirements.
- e. Women capable of becoming pregnant who are continuously not heterosexually active are exempt from contraceptive requirements. However, they must still undergo pregnancy testing as described in inclusion criterion “4a”.

